7.0 Protocol Treatment

7.1 Treatment Schedule

| Agent | Dose | Route | Days | Max. No. of cycles |
|-----------|-----------|-------|------|--------------------|
| Ibrutinib | 420 mg QD | Oral | 1-28 | 36 |

Cycle length = 28 days

7.11 Ibrutinib

- 420mg PO QD will begin on day one of cycle #1.
- Four weeks will constitute 1 treatment cycle.
- Patients will be evaluated for MRD status every 3 cycles (as discussed previously in Section 4.0, footnote 8, see detailed MRD section 11.4).
- A maximum of 36 cycles of maintenance cycles will be given.
- Treatment will be discontinued if (a) patients develop unacceptable side effects, (b) if patients develop disease progression while on ibrutinib maintenance (recommended to be confirmed on two independent occasions at least 2 week apart and consistent with the IWCLL guidelines, see Section 11.0), (c) if patients have completed the 36 cycles on maintenance therapy, (d) if the patient is removed from the study by the treating physician due to concern of overall wellbeing and in the best interest of the patient, (e) patients who have residual disease at the end of 36 cycles will continue to event monitoring

7.2 Treatment by Local Medical Doctor (LMD): If patient is tolerating therapy without excessive toxicity at a stable dose level after 1 cycle (can be confirmed through telecommunication and does not need to be physically evaluated at Mayo Clinic) of treatment the patient may be seen by their primary physician (if outside of Mayo Clinic). Results would need to be returned to Mayo Clinic. Patient would need to return to Mayo Clinic every 3 cycles for follow-up at Mayo Clinic.

7.3 After the first 6 months, clinical evaluation and blood tests can be obtained per test schedule and mailed/faxed to Mayo Clinic and patient can return at least every 3 cycles for follow up to Mayo (patient does not need to be seen every cycle). Patient may be seen more frequently, as clinically necessary. All unused study drug must be returned, and all study drug must be accounted for. A 3-month supply of study drug may be provided at each cycle.

8.0 Dosage Modification Based on Adverse Events

8.1 Dose Levels (Based on Adverse Events in the Tables below)

| Dose Level | Ibrutinib |
|------------|--------------|
| 0* | 420 mg daily |
| -1 | 280 mg daily |
| -2 | 140 mg daily |

* Dose level 0 refers to the starting dose.

8.2 Dose Modification

Omit = The current dose(s) for the specified drug(s) during a cycle is skipped. The patient does not make up the omitted dose(s) at a later time

Hold/Delay = The current dose(s) of all drugs during a cycle is delayed. The patient does make up the delayed dose(s) when the patient meets the protocol criteria to restart drugs.

Discontinue = The specified drug(s) are totally stopped.

| Use the NCI Common Terminology Criteria for Adverse Events (CTCAE) version 4.0 (section 10.1) unless otherwise specified. | | | |
|---|--|-----------|---|
| CTCAE System/Organ/Class (SOC) | ADVERSE EVENT | AGENT | ACTION |
| AT TIME OF RETREATMENT | | | |
| Investigations | Neutrophil count decreased Grade 4 lasting >7 days | | Hold (day 1) or omit (days 2-28) Ibrutinib until recovery to Grade ≤ 1 or baseline; may restart at original dose for first occurrence. Each subsequent occurrence may restart at next lower dose after recovery to Grade ≤ 1 or baseline. If AE occurs at lowest dose discontinue treatment. NOTE: Baseline cytopenia: In patients whose baseline (i.e., prior to starting protocol therapy) ANC is 1000/ μ L, the above Ibrutinib dose modifications, if required, would not be applied until Cycle 3. |
| Blood and lymphatic system disorders | \geq Grade 3 Febrile neutropenia | Ibrutinib | Hold (day 1) or omit (days 2-28) Ibrutinib until fever resolves and ANC \geq 1000/ μ L, then resume Ibrutinib at the previous dose. |
| Gastrointestinal disorders | \geq Grade 3 Nausea (if persistent despite optimal antiemetic therapy) \geq Grade 3 Vomiting (if persistent despite optimal antiemetic therapy) \geq Grade 3 Diarrhea (if persistent despite optimal anti-diarrheal therapy) | | Hold (day 1) or omit (days 2-28) Ibrutinib until recovery to Grade ≤ 1 or baseline; may restart at original dose for first occurrence. Each subsequent occurrence may restart at next lower dose after recovery to Grade ≤ 1 or baseline. If AE occurs at lowest dose discontinue treatment. |
| Other non-hematologic | Any other Grade 4 AE or any unmanageable Grade 3 AE | | |

- **Dose delay:** Ibrutinib may be held for toxicity considerations for a maximum of 28 consecutive days. Study medication should be discontinued permanently in the event of a toxicity lasting more than 28 days. If Ibrutinib is interrupted for a reason other than toxicity (e.g. unrelated illness) it must be restarted within 90 days. If interrupted for more than 90 days, study medication should be discontinued permanently and go to event monitoring.
- **Dose re-escalation:** Patients who require a dose reduction during a given cycle will remain at that dose for at least 2 additional cycles. **At the investigator discretion, the dose of ibrutinib may be re-escalated after 2 cycles of a dose reduction in the absence of a recurrence of the toxicity that led to this reduction.** This is particularly reasonable based upon the long-term safety data now available in ibrutinib treated patients that show that most of the hematological or non-hematological AEs either decreased or remained stable (see investigator brochure section 5.3).

- If multiple adverse events are seen, administer dose based on the greatest reduction required by any single adverse event observed.
- Dose modifications are for adverse events attributed to study treatment only. Dose modifications are not required for adverse events if they are deemed unrelated to study treatment.
- Reductions apply to treatment given in the preceding cycle and are based on adverse events observed since the prior dose.
- If cough, dyspnea, and other pulmonary symptoms occur, a chest x-ray and high-resolution chest CT scan should be obtained. Incentive spirometry studies (to include DLCO) should be considered. Consider Pneumocystis pneumonia or viral pneumonitis.

8.3 **Dose Modification for Hematological Toxicities (Platelet and Hemoglobin only)**

Note: hematological toxicity is not based on CTCAE 4.0 except neutrophil but based on CLL specific hematological toxicity (this table and Appendix V).

Dose modification guidelines for drug-related hematological (hemoglobin and platelets) adverse events

| Toxicity | Grade ¹ , ² | Decrease from pretreatment | Hold Treatment (Y/N) | Timing for restarting treatment | Dose/Schedule for restarting treatment | Discontinue Subject (after consultation with PI) |
|--|--------------------------------------|-----------------------------------|----------------------|--|---|--|
| CLL/NHL specific Hematological Toxicity (Appendix V) | 1 | 11-24% decrease in HGB or PLT | No | N/A | N/A | N/A |
| | 2 | 25-49% decrease in HGB or PLT | | | | |
| | 3 | 50-74% decrease in HGB or PLT | Yes | Toxicity resolves to Grade 0-1 or baseline | Hold (day 1) or omit (days 2-28) Ibrutinib until recovery to Grade \leq 1 or baseline | Toxicity does not resolve within 8 weeks of last treatment |
| | 4 | \geq 75% decrease in HGB or PLT | Yes | Toxicity resolves to Grade 0-1 or baseline; may restart at original dose for first occurrence. Each subsequent occurrence may restart at next lower dose after recovery to Grade \leq 1 or baseline. If AE occurs at lowest dose, discontinue treatment. | | Permanent discontinuation should be considered for any severe or life-threatening event. Go to event monitoring if \geq 1 cycle of therapy was given, otherwise go to observation. |

¹ If, at any level of decrease the platelet count is $< 20,000/\mu\text{L}$, this will be considered grade 4, unless the initial platelet count was $\leq 20,000 \mu\text{L}$ in which case the patient is inevaluable for toxicity referable to platelet counts.

² If, at any level of decrease from the baseline value the platelet and/or hemoglobin counts are within normal limits, this will be considered a grade 0.

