Diarrhea: Approximately one-third of subjects treated with ibrutinib monotherapy and two-thirds treated with combination therapy reported diarrhea. Other frequently reported gastrointestinal events include nausea, vomiting, and constipation. These events are rarely severe, with only a small number of Grade 3 events, and no Grade 4 events reported to date.

Summary:

Pooled safety data for subjects treated with ibrutinib monotherapy in 11 nonrandomized studies (PCYC-1102-CA, PCYC-1117-CA, PCYC-1112-CA [crossover only], PCYC-1104-CA, PCI-32765MCL2001, PCI-32765MCL4001, PCYC-1106-CA, PCYC-1111-CA, PCI-32765FLR2002, PCYC-04753, and PCI-32765-JPN-101) has been evaluated (ibrutinib Investigator's Brochure [IB], version 8.0, dated 24 June 2014).

The most frequently reported treatment-emergent adverse events in more than 10% of subjects receiving ibrutinib as monotherapy in nonrandomized studies (N=1061) were diarrhea (35.9%), fatigue (28.6%), nausea (20.2%), cough (17.5%), and anemia (15.2%).

The most commonly reported Grade 3 or 4 adverse events that were hematologic in nature were neutropenia (10.7%), thrombocytopenia (6.2%), and anemia (5.5%).

Pneumonia (5.7%), fatigue (2.9%), hypertension (2.7%), and atrial fibrillation (2.6%) were the most frequently reported nonhematologic Grade 3 or 4 adverse events.

The incidence of treatment-emergent SAEs reported was 41.3% (N=1061); pneumonia (7.0%), atrial fibrillation (2.8%), and febrile neutropenia (2.3%) were the most commonly reported treatment-emergent SAEs .

In a randomized Phase 3 study in subjects with CLL/SLL (PCYC-1112-CA), the most frequently reported treatment-emergent adverse events in the ibrutinib arm were diarrhea (47.7%), fatigue (27.7%), nausea (26.2%), pyrexia (23.6%), anemia (22.6%), and neutropenia (21.5%). Adverse events reported at a higher incidence (> 10% difference) in the ibrutinib arm than in the ofatumumab arm included diarrhea (ibrutinib: 47.7%, ofatumumab: 17.8%), arthralgia (17.4%, 6.8%), and petechiae (13.8%, 1.0%).

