The most commonly reported Grade 3 or 4 adverse events in more than 2% of ibrutinib treated subjects that were hematologic in nature were neutropenia (16.4%), thrombocytopenia (5.6%), and anemia (4.6%). Pneumonia (6.7%) was the most frequently reported nonhematologic Grade 3 or 4 adverse event. The most frequently reported SAEs in ibrutinib subjects were pneumonia (8.7%), atrial fibrillation (3.1%), pyrexia (3.1%), lung infection (2.6%), lower respiratory tract infection (2.1%) and urinary tract infection (2.1%).

For more detailed information refer to the current version of the IB.

Long-term use and safety: Analysis of adverse events over a 3-year follow-up period is now available (see *Investigator Brochure for details, Item 5.3.1.4; IB-v8_24June2014_v1.2*) and shows that most AEs of clinical interest, including hematological and non-hematological AEs, either decreased or stayed the same overtime.

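### Sections 8.2 and 8.3 set different discontinuation points for prolonged platelet or hemoglobin toxicity (28 days against 8 weeks), with no stated precedence and no definition of last treatment

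*Combined protocol and SAP*

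**What the plan says.** The dose-delay bullet of Section 8.2 contains two linked statements. The first caps the interruption: "Ibrutinib may be held for toxicity considerations for a maximum of 28 consecutive days". The second gives the consequence: "Study medication should be discontinued permanently in the event of a toxicity lasting more than 28 days". Neither is restricted by type or grade of toxicity. The only longer limit in that bullet, 90 days, applies to interruptions for reasons other than toxicity.

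Section 8.3 is headed as covering platelets and hemoglobin only. Its table has separate columns for holding, restarting and discontinuing. Under the discontinuation column, which requires consultation with the PI, the entry printed against grade 3 (a 50-74% decrease) reads: "Toxicity does not resolve within 8 weeks of last treatment". The grade 4 entry says that permanent discontinuation should be considered for severe or life-threatening events and gives no number of days or weeks. Table cells may have been merged in the layout, so the 8-week entry may also span grade 4. That uncertainty is not part of the criticism.

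The note above the 8.3 table says which grading scale applies. It does not mention the 28-day limit.

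**The concern.** These are two stated stopping points for the same kind of event, and they differ by a factor of two. A platelet or hemoglobin toxicity is a toxicity in the sense of 8.2, so both passages apply to it on their face. The protocol gives no rule for choosing between them.

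The main stake is consistent safety management: patients with the same course could be stopped permanently or kept eligible to restart, depending on which section the investigator opens. There is a possible knock-on effect on the analysis. Sections 16.323 and 16.324 leave out of the landmark comparisons any patient who discontinues before 48 weeks, so an inconsistent stopping rule could change who enters those two comparisons.

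**Working it through.** The plan states no statistical figure on this point, so there is none to reproduce. The check compares the two limits in days.

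**Inputs**
- Section 8.2: maximum hold for toxicity, and duration of toxicity beyond which treatment stops: 28 days.
- Section 8.3: 8 weeks, counted from last treatment.
- Section 7.1: daily dosing in 28-day cycles.

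**Step 1: common units.** 8 weeks × 7 = 56 days. 56 − 28 = 28 days of difference, before asking where each count begins.

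**Step 2: what last treatment could mean.** Section 8.3 does not say. Usage elsewhere varies: the MRD footnote to Section 4.0 refers both to the last treatment cycles and to the last treatment dose, and Section 10.4 counts from the last administration. Let d be the cycle day of the first missed dose, with d = 29 meaning day 1 of the next cycle.

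| Meaning of last treatment | Days off drug before the 8.3 point | Result | Compared with 28 days |
|---|---|---|---|
| Last dose taken | 56 | 56 | 28 longer |
| Day 1 of the last cycle started | 56 − (d − 1) | 55 (d = 2) down to 28 (d = 29) | 27 longer, down to equal |
| Last day of the last cycle | (28 + 56) − (d − 1) | 83 (d = 2) down to 56 (d = 29) | 55 longer, down to 28 longer |

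The limits coincide in only one case: last treatment means day 1 of the last cycle started, and the hold begins on day 1 of the following cycle.

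**Step 3: the conflict under the last-dose reading.** With daily dosing this is the natural reading, but it is an assumption.
- Hold of 28 days or fewer: neither point is reached.
- Hold of 29 to 56 days: permanent discontinuation under 8.2; the 8.3 point is not reached.
- Unresolved beyond 56 days: both sections reach discontinuation.

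The conflict is therefore confined to the middle band. Toxicities that never resolve do not count towards it.

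**Step 4: is there a precedence rule?** The 8.3 note settles grading only. The neighbouring 8.2 bullets are not confined to non-hematologic events: the re-escalation bullet mentions hematological and non-hematological events together. No sentence in either section sets one limit above the other.

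**Step 5: effect on the design.** The decision rule in Section 16.211 (at least 4 successes in 32) and the table in Section 16.24 depend only on the sample size, the cut-off and the assumed success proportion. The binomial probabilities P(X ≥ 4 | n = 32, p) at p = 0.05, 0.10, 0.15 and 0.20 are 0.0738, 0.3997, 0.7279 and 0.9069. They match the printed 0.07, 0.40, 0.73 and 0.91, and no treatment-hold limit enters them. Section 16.11 excepts otherwise eligible, treated patients from the denominator only for a major treatment schedule violation, so stopping for toxicity does not by itself remove a patient.

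**The case against.** The best defence is that 8.3 is the specific section and displaces the general one. It is limited to platelets and hemoglobin, it has its own hold, restart and discontinuation columns, and the table in 8.2 lists neither platelets nor hemoglobin. Its discontinuation column also requires consultation with the PI, which provides a check before the action. This is a reasonable inference and it narrows the ambiguity. It does not remove it, because the 8.2 wording is unqualified and the protocol never states that inference.

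It can also be said that 8.2 uses should for permanent discontinuation, which leaves some discretion. That is fair for the second statement, but the hold limit beside it is expressed as a maximum.

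Three stronger readings are tempting and are not supported:

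- **That 8.2 counts from the onset of toxicity**, which would lengthen the conflict whenever onset precedes the last dose. Section 8.2 does not mention onset. Its sentence follows directly on the hold limit and can be read as toxicity that keeps the drug on hold beyond 28 days.
- **That the number of affected patients can be estimated from the background safety data.** Section 1.2 gives grade 3 or 4 thrombocytopenia and anemia rates of 6.2% and 5.5% (pooled monotherapy) and 5.6% and 4.6% (the randomized phase 3 study). These come from other populations, combine two grades, are not restricted to drug-related events, are not stated to use the CLL grading scale, and carry no durations. Any proportion lasting between 29 and 56 days would have to be invented.
- **That the primary conclusion could turn on this.** A patient stopped early has fewer on-treatment assessments, but nothing in the documents shows that such a patient would otherwise have become a success.

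**Conclusion.** The contradiction is real and limited. Sections 8.2 and 8.3 give 28 days and 56 days as discontinuation points for overlapping events, no sentence says which governs, and the start of the 8-week period is undefined. Under the last-dose assumption, holds of 29 to 56 days receive opposite answers. Under other readings the gap ranges from none to 55 days, which shows how much depends on the missing definition.

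The finding relies on the single 8-week entry in the 8.3 table. Whether that entry covers grade 3 alone or also grade 4 remains open.

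The number of patients cannot be derived. It is probably small, since it requires a severe, drug-related platelet or hemoglobin toxicity with a duration inside a particular band, in a study of at most 35 patients. Alpha, power and the primary denominator do not change. An effect on the landmark analyses is possible only for discontinuations in the first 12 of up to 36 cycles (12 × 28 days = 48 weeks), and it is not shown to occur. The matter concerns consistent safety management and clear wording; it is not a flaw in the statistical design.

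**What to change.** The sponsor and investigator should reconcile Sections 8.2 and 8.3 so that one reading is possible. The amended text should state:

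- which limit governs platelet and hemoglobin toxicity;
- to which grades it applies;
- from what start point time is counted, with last treatment either defined or replaced by a defined term.

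Which limit is appropriate is a clinical decision for the sponsor and investigator, and none is proposed here. The cost is amended protocol wording, with no change to sample size, decision rule, assessments or analysis methods.

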8.4 Dose Modification for Hepatic Impaired Subjects

Ibrutinib is metabolized in the liver and therefore subjects with clinically significant hepatic impairment at the time of screening (Child- Pugh class B or C) are excluded from study participation. For subjects who develop mild liver impairment while on study (Child-Pugh class A), the recommended dose reduction for ibrutinib is to a level of 280 mg daily (two capsules). For subjects who develop moderate liver impairment while on study (Child-Pugh class B), the recommended dose reduction is to a level of 140 mg daily (one capsule). Subjects who develop severe hepatic impairment (Child-Pugh class C) must hold study drug until resolved to moderate impairment (Child-Pugh class B) or better. Monitor subjects for signs of toxicity and follow dose modification guidance as needed (Refer to Appendix VII).

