3.29b Requires treatment with a strong cytochrome P450 modulators (CYP3A inhibitor and/or CYP3A inducers) [see Section 9.5(a)]. NOTE: A comprehensive list of inhibitors, inducers, and substrates may be found at <http://medicine.iupui.edu/clinpharm/ddis/main-table/>. This website is continually revised and should be checked frequently for updates.

3.29c Currently active, clinically significant hepatic impairment Child-Pugh class B or C according to the Child Pugh classification (see Appendix VII)

- 3.29d Major surgery \leq 4 weeks prior to registration.
- 3.29e Patients who have active infectious hepatitis.
- 3.29f Patients with other diseases that in the opinion of the treating physician pose a higher risk for treatment with ibrutinib therapy including active HIV infection and bleeding disorders.

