d) Excretion –The excretion of ibrutinib is predominantly via the feces with approximately 80% recovered mostly within 2 days, whereas ~8% is excreted in urine. Approximately 1% of the ibrutinib is recovered as unchanged drug, all in feces. Overall, these PK characteristics resulted in minimal accumulation of both parent compound and metabolite PCI-45227 on repeated daily dosing of ibrutinib.

e) Special populations: a small increase in bioavailability was estimated with increasing age. Exposure is predicted to increase approximately 14% and decrease approximately 20% in subjects of 81 and 49 years of age, compared to a typical 67-year old subject. No statistically significant effects were observed for the other covariates tested, i.e., sex, race, mild and moderate renal impairment, mild hepatic impairment and B-cell histology. The recommended doses for patients with mild and moderate liver impairment are 280 mg/day and 140 mg/day (Child-Pugh Class A and B, respectively). It is not recommended to administer ibrutinib to subjects with severe hepatic impairment (Child-Pugh Class C).

15.16 **Potential Drug Interactions:** Ibrutinib is primarily metabolized by cytochrome P450 enzyme 3A4/5. Voriconazole and posaconazole can be used concomitantly with ibrutinib as per the dosing guidance described in the specific clinical study protocol. All other strong inhibitors of CYP3A (eg, ketoconazole, indinavir, nelfinavir, ritonavir, saquinavir, clarithromycin, telithromycin, itraconazole, nefazodone, and cobicistat) should be avoided, and an alternative with less CYP3A inhibitory potential should be considered. If the benefit outweighs the risk and a strong CYP3A inhibitor must be used, see the recommended dose modifications described in the specific clinical study protocol.

If a moderate CYP3A inhibitor (eg, fluconazole, erythromycin, amprenavir, aprepitant, atazanavir, ciprofloxacin, crizotinib, diltiazem, fosamprenavir, imatinib, verapamil, amiodarone, dronedarone) is indicated in patients with B-cell malignancies, reduce the ibrutinib dose to 280 mg for the duration of the inhibitor use or as per recommended dose modifications described in the specific clinical study protocol. No ibrutinib dose modifications for moderate inhibitors are required in patients with cGVHD dosed with ibrutinib 420 mg.

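### A patient who enters with mild hepatic impairment (Child-Pugh A) starts at 420 mg under 7.11, whereas 15.15(e) recommends 280 mg

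*Combined protocol and SAP*

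**What the plan says.** **Eligibility.** The hepatic exclusion in 3.29c is "Currently active, clinically significant hepatic impairment Child-Pugh class B or C". Section 8.4 repeats it for screening. Class A is not excluded. Section 3.19 limits total bilirubin to 1.5 mg/dL (patients with Gilbert's syndrome may qualify on direct bilirubin) and allows AST and ALT up to 3.5 times the upper limit of normal.

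**Starting dose.** Section 7.11 states "420mg PO QD will begin on day one of cycle #1". The table in 7.1 gives the same dose. Section 8.1 lists 420, 280 and 140 mg as levels 0, -1 and -2, and notes that "Dose level 0 refers to the starting dose". None of these places makes an exception for the liver.

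**Impairment that arises on study.** Section 8.4 reads "For subjects who develop mild liver impairment while on study (Child-Pugh class A), the recommended dose reduction", and the level it names is 280 mg daily. It sets 140 mg for moderate impairment (class B) and a hold for severe impairment (class C).

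**Drug information.** Section 15.15(e), on special populations, states "The recommended doses for patients with mild and moderate liver impairment are 280 mg/day and 140 mg/day", for class A and class B respectively. It says nothing about when the impairment began.

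**The concern.** Two patients with the same mild hepatic impairment get different instructions according to when it appeared. If it develops after enrolment, 8.4 reduces the dose to 280 mg. If it was known at enrolment, 7.11 starts the patient at 420 mg, no later rule in Sections 7 or 8 revisits that dose for the impairment itself, and 15.15(e) points to 280 mg. An investigator with such a patient has two doses in one document and nothing that says which applies. At stake are consistent dosing of an eligible patient and a clear record of what counts as the protocol dose.

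**Working it through.** No statistical quantity is involved, so the check sets the sections side by side and adds short arithmetic.

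**1. Child-Pugh range (Appendix VII).** There are five measures, each scored 1 to 3.
- Minimum: 5 x 1 = 5. Maximum: 5 x 3 = 15. This reproduces the appendix's span (5-6 = A, 7-9 = B, 10-15 = C).
- There are 3^5 = 243 score combinations: 6 in class A, 90 in class B and 147 in class C.
- The six class A combinations are the all-normal one (score 5) and five with a single measure at 2 points (score 6).

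**2. Can a class A patient enrol?** Yes.
- Bilirubin at or below 1.5 mg/dL scores 1 point, because the first band is below 2 mg/dL. That leaves five of the six class A combinations open to a patient without Gilbert's syndrome: all normal, or one of albumin, INR, ascites and encephalopathy at 2 points.
- Nothing in 3.19 or 3.29c bars these combinations. Whether 3.23, 3.29e or 3.29f bars a given patient depends on the case.

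**3. Dose by section for mild impairment (class A)**

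| Situation | Section | Dose |
|---|---|---|
| Present at entry | 7.1, 7.11, 8.1 | 420 mg |
| Develops on study | 8.4 | 280 mg |
| Onset not specified | 15.15(e) | 280 mg |

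**4. Size of the difference**
- 420 - 280 = 140 mg per day; 420 / 280 = 1.5; 1 - 280/420 = 33.3% lower.
- Per 28-day cycle: 420 x 28 = 11,760 mg against 280 x 28 = 7,840 mg.
- Reduction steps left under 8.1: two from 420 mg (280, 140), one from 280 mg (140).

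**5. What a correction must not catch**
- An all-normal score of 5 is class A, so the class label alone cannot define the group.
- AST and ALT are not Child-Pugh measures, so a rise within the 3.19 limit does not move the score.
- A patient with Gilbert's syndrome whose total bilirubin is 2-3 mg/dL scores 2 + 4 x 1 = 6 from that alone.

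**6. Can the class be assigned from scheduled tests?** Not fully. The chemistry group in Section 4.0 includes bilirubin but lists neither albumin nor PT INR. The allowance in footnote 6 for extra tests when clinically indicated refers to cycles after the first two, so it does not cover baseline.

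**7. Design figures.** Section 16.24 depends on 32 patients, a cut-off of 4 successes and the true success proportion. Starting dose is not an input, so the stated significance level and power stand.

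**The case against.** The best defence is that Section 15 is background and Sections 7 and 8 govern. Section 15 does read as generic drug text: 15.16 discusses a graft-versus-host indication, and 15.19 mentions combination with a drug that is not part of this trial's treatment. For strong CYP3A inhibitors, 15.16 sends the reader back with "see the recommended dose modifications described in the specific clinical study protocol". On this view 8.4 is complete: class B and C are excluded at screening, later impairment is reduced, and a class A patient at entry is meant to receive 420 mg. Section 15.15(e) itself reports "No statistically significant effects were observed for the other covariates tested, i.e., sex, race, mild and moderate renal impairment, mild hepatic impairment". Sections 3.23, 3.29e and 3.29f can keep doubtful patients out, and 8.4 asks for toxicity monitoring.

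Part of this stands. The sponsor may intend 420 mg, and the covariate statement bars any claim that 420 mg is harmful here. The conflict remains, for four reasons:
- 15.15(e) has no clause deferring to the protocol.
- It recommends 280 mg directly after the covariate statement.
- 8.4 adopts the same 280 and 140 mg values, which makes a deliberate 420 mg for mild impairment at entry hard to infer.
- The eligibility provisions set no starting dose for a patient who does enrol, and the 8.2 rules apply only to adverse events attributed to study treatment, which impairment present at entry is not.

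A reader might also infer that the mild step in 8.4 is unworkable because every patient with a normal liver is already class A. The documents do not support that. Section 8.4 ties the class to the development of mild liver impairment on study, and a patient who scores 5 throughout with a normal liver has developed none. The class B and C steps are unaffected.

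**Conclusion.** The inconsistency holds and is minor. For clinically established class A impairment at entry, the dosing sections give 420 mg and 15.15(e) gives 280 mg, a ratio of 1.5, and no text reconciles them. This assumes that 15.15(e) means what it says without limit on onset, and that the patient meets every other criterion.

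Two stronger conclusions are not supported:
- **A demonstrated safety problem.** Section 15.15(e) reports no statistically significant effect of mild hepatic impairment, and the documents give no evidence of harm at 420 mg in such patients.
- **A count of patients affected.** None can be derived. The 35 in 16.22 is projected accrual rather than a hard cap, since 16.212 and 16.34 provide for over-accrual. The number is probably small, because 3.19, 3.23, 3.29e and 3.29f narrow the group.

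Alpha, power and sample size are unchanged.

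**What to change.** Add one sentence to 7.11: *Patients with clinically established mild hepatic impairment at baseline (Child-Pugh class A; not a normal score of 5, isolated transaminase elevation within 3.19, or Gilbert's syndrome alone) start at 280 mg daily (dose level -1).* If the sponsor intends 420 mg for these patients, state that in 15.15(e) instead.

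Costs: probably few patients receive a lower dose, and they have one reduction step left instead of two. Where baseline impairment is known or suspected, albumin and PT INR may need to be drawn to assign the class. Footnote 6 does not cover this, so the new sentence or a test-schedule footnote should allow it. The medication diary in Appendix VI, preprinted at 420 mg, would need the dose changed for these patients. Design and analysis are untouched.

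Optional clarification only: 8.4 could note that a normal score of 5 is class A and does not by itself trigger the mild-step reduction.
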